# 7.2.3 Eligibility assessments

#### 7.2.3.1 Structured Clinical Interview for DSM-5 - Clinical Trial Version (SCID-5)

The SCID-5 is a semi-structured interview guide for making the major DSM-5 diagnoses. It is conducted by a clinician or trained mental health professional who is familiar with the DSM-5 classification and diagnostic criteria.

The SCID-5 Eating Disorder module will be conducted at Screening to diagnose BED and to exclude other eating disorders e.g., anorexia nervosa and bulimia nervosa.

ACT-539313		Doc
Binge Eating Disorder		
Protocol ID-082A201	Confidential	
Final Version 3		
4 May 2021, page 65/140		

# 7.2.3.2 Eating Disorder Examination Questionnaire (EDE-Q)

The EDE-Q is a 28-item scale that assesses attitudinal and behavioral dimensions of the eating psychopathology in BED. It will be used to confirm the SCID-5 diagnosis of BED. EDE-Q focuses on the previous 28 days, except for the diagnostic items that are rated for the durations stipulated in the DSM-5 (SCID-5). The EDE-Q also assesses in more detail the frequency of different forms of overeating, including objective bulimic episodes (binge eating defined as unusually large quantities of food with a subjective sense of loss of control) and subjective bulimic episodes (defined as a subjective sense of loss of control but a normal or small amount of food).

The EDE-Q will be answered by the study participant and reviewed by a clinician or trained mental health professional to confirm the diagnosis of BED as well as to confirm the self-reported severity of binge eating in BE days, based on the last 28 days. The full EDE-Q (28-item) version will be assessed at Visit 1.

# 7.2.3.3 Mini International Neuropsychiatric Interview©

The MINI© is a psychiatric examination [Sheehan 1999] used to identify study participants with exclusionary psychiatric conditions. The MINI© will be conducted at Screening by a trained clinician. The MINI© will be conducted to ascertain the psychiatric diagnoses, and any clinically relevant psychiatric conditions will be reported in the eCRF.

# 7.2.3.4 Binge Eating Diary

The number of BE episodes will be recorded by the study participant daily, preferably in the evening, for at least 2 weeks prior to randomization in a paper-based diary. The diary captures the number of binges per day, total time spent BE each day, type of binge (mealtime vs non-mealtime), and a description of the binge (amount and types of food). A BE day is defined as a day with at least one BE episode. These data will be reviewed by the investigator with the study participant at Visit 2 and will determine whether the participant meets inclusion criterion 9. The investigator will confirm whether each recorded eating episode is a binge or not. The number of confirmed binges each day will also be recorded in the eCRF.

# 7.2.4 Efficacy assessments

The schedule of activities is presented in Table 1.

# 7.2.4.1 Binge Eating Diary

As above, the number of BE episodes will continue to be recorded by the study participant daily, preferably in the evening, until end of study treatment. Data from the diary will be reviewed by the investigator with the study participant at each visit until end of study treatment and will help the investigator confirm whether each recorded eating episode is a

ACT-539313		Doc No D-21.148
Binge Eating Disorder		
Protocol ID-082A201	Confidential	
Final Version 3		
4 May 2021, page 66/140		

binge or not. The number of confirmed binges each day must be recorded in the eCRF. A BE day is defined as a day with at least one BE episode.

# 7.2.4.2 Yale-Brown Obsessive-Compulsive Scale Modified for Binge Eating

The YBOCS [Goodman 1989] is an interviewer-administered assessment developed to measure the severity of obsessive-compulsive symptoms in patients with a diagnosis of OCD. The YBOCS-BE is a version of the YBOCS modified to measure the obsessiveness of BE thoughts and the compulsiveness of BE behaviors. The BE behavior of BED is similar to an OCD compulsion in that it is time-consuming, distressing, may inhibit or hinder functioning, and may or may not be successfully resisted [Deal 2015]. The scale has been modified by replacing the term "obsessive thoughts" with "thoughts, impulses, or ideas to binge eat" for the first 5 items, and "compulsive behaviors" with "binge eating" for items 6–10. The 10 items are clinician/investigator-rated on a 5-point Likert scale. The YBOCS-BE [Machado 2020,Yee 2019] will be administered on a touchscreen device on site, at Visit 2 (Randomization), Visit 5 (Week 4), Visit 7 (Week 8), and EOT (Week 12).

# 7.2.4.3 Clinical Global Impression of Severity Scale

The CGI-S is a 1-item, 7-point scale that requires the investigator to rate the severity of the study participant's illness at the time of assessment, relative to the clinician's experience with patients who have the same diagnosis.

After a clinical evaluation, the CGI-S form can be completed in less than a minute by an experienced rater. In practice, the CGI-S captures clinical impressions that transcend mere symptom checklists. It ranges between "Normal, not at all ill" and "Among the most extremely ill patients". The CGI-S will be administered on a touchscreen device on site, at Visit 1 (Screening), Visit 2 (Randomization), Visit 5 (Week 4), Visit 7 (Week 8), and EOT (Week 12).

# 7.2.4.4 Clinical Global Impression of Change Scale

The CGI-C is a 1-item, 7-point scale that requires the clinician to assess how much the study participant's illness has improved or worsened relative to a baseline state at the beginning of the intervention. The range is between "Very much improved" and "Very much worse". The CGI-C will be administered on a touchscreen device on site at Visit 3 (Week 1), Visit 5 (Week 4), Visit 7 (Week 8), and EOT (Week 12).

#### 7.2.4.5 Patient Global Impression of Severity scale

The PGI-S is a question concerning the overall severity of symptoms and impact that the study participant may have experienced due to his/her BE episodes over the 7 days preceding the PGI-S completion.

ACT-539313		Doc No D-21.148
Binge Eating Disorder		
Protocol ID-082A201	Confidential	
Final Version 3		
4 May 2021, page 67/140		

It ranges between "No binge eating" and "Very severe". It is a self-administered questionnaire completed on a touchscreen device on site at Visit 2 (Randomization), Visit 5 (Week 4), Visit 7 (Week 8), and EOT (Week 12).

# 7.2.4.6 Patient Global Impression of Change scale

The PGI-C is a 1-item, 7-point scale that asks the study participant to evaluate all aspects of his/her health and to assess if there has been an improvement or decline in clinical status from the baseline of the observation.

The scale starts at "Very much worse" escalating to "Very much improved". The PGI-C will be administered on a touchscreen device on site at Visit 3 (Week 1), Visit 5 (Week 4), Visit 7 (Week 8), and EOT (Week 12).

# 7.2.4.7 Eating Disorder Examination Questionnaire (EDE-Q7)

The EDE-Q7 is a self-reported questionnaire containing 7 out of the 28 questions from the EDE-Q about eating behaviors (Items #1, 3, 4, 22, 23, 25 and 26). It will be completed on a touchscreen device on site at Visit 2 (Randomization), Visit 5 (Week 4), Visit 7 (Week 8), and EOT (Week 12).

# 7.2.4.8 Hamilton Depression Rating Scale (HAMD-17)

The HAMD-17 [Hamilton 1960] will be used to provide an indication of depression. The total score will be used to exclude study participants with symptoms of depression of at least moderate severity at baseline (score of 17 or more). In addition, it will also be used to assess the change from baseline to Weeks 6 and 12 on the total score in study participants who may have signs of depressive symptoms as well as on its anxiety-related subitems 10 & 11 and the MPS. The MPS combines the items 1, 2, 7, 8, 9, and 10 and is an observational rating measure to assess the severity of depressive symptoms and its improvement under therapy. It will be completed on a touchscreen device on site at Visit 1 (Screening), Visit 2 (Randomization), Visit 6 (Week 6), EOT (Week 12), and EOS.

# 7.2.4.10 Body weight and height

Body weight will be measured at all visits up to EOT and recorded in the eCRF. Height will only be measured at Screening. Body weight measurements will be done in lightweight clothes, without shoes, with an empty bladder, and approximately at the same time of the day. The same calibrated scale should be used throughout the trial.

The BMI will be calculated at Visit 1 (for eligibility) and displayed automatically upon entry of weight and height in the eCRF.

Unless otherwise specified, the date of each assessment will be collected in the eCRF.

# 7.2.5 Safety assessments

Unless otherwise specified, the date of each assessment will be collected in the eCRF.

The definitions, reporting, and follow-up of AEs, SAEs and pregnancies are described in Section 8.

#### 7.2.5.1 Physical examination

Physical examination includes the examination of the general appearance (heart, lungs, abdomen, skin, extremities, eyes, ears, nose, throat, lymph nodes, nervous system, etc.). Physical examination is to be performed at Visit 1 and at EOT visit.

Other examinations will be performed if indicated, based on medical history and/or symptoms.

Information for all physical examinations must be included in the source documentation at the study site.

The physical examination will be reported in the eCRF as either normal or abnormal; in the latter case, the investigator should specify whether it is clinically relevant. Clinically relevant findings (other than those related to BED) that are present prior to signing the ICF must be recorded as medical history in the eCRF. Physical examination findings, which meet the definition of an AE [Section 8.1.1] and are made after signing of the ICF, must be recorded on the AE form of the eCRF.

#### 7.2.5.2 Vital signs

Oral or axillary temperature, pulse rate, respiratory rate, and blood pressure (systolic and diastolic) will be assessed and recorded in the eCRF. The date and actual time of vital sign measurements will be entered in the eCRF. Any clinically significant abnormal vital sign

value should be repeated after a reasonable interval (e.g., 10–15 min) to ensure accuracy. If the abnormality persists upon repeat measurement, the participant should be assessed by the investigator.

Blood pressure and pulse measurements will be assessed with the study participant in a seated position. It is recommended to allow the study participant to rest for at least 5 minutes in a quiet setting without distractions (e.g., television, cell phones), and to use the same position (i.e., sitting), same device and same arm throughout the study for an individual study participant.

Vital signs are to be assessed at each visit until EOT visit.

#### 7.2.5.3 Electrocardiograms

A standard 12-lead ECG will be performed at Visit 1 (Screening) and EOT visit using the ECG machine provided by the central ECG vendor. ECGs will be performed with the study participant in a fully rested supine position after the study participant has been allowed to rest for a minimum of 5 minutes. The date and actual time of ECGs will be recorded in the eCRF.

A central ECG vendor (see ECG manual for contact details) will be used for the evaluation of all protocol-mandated ECGs, including re-tests due to ECG abnormalities and ECGs performed at unscheduled visits. The site personnel will electronically transmit the ECGs to the central ECG vendor for central reading.

The 12-lead ECG measurements (e.g., HR and the intervals PR, QRS, QT, QTcF, and QTcB), qualitative ECG findings (e.g., rhythm, ectopy, conduction and morphology) and the overall interpretation of the ECG (normal/abnormal) will be provided by the ECG central vendor.

ECG reports will be provided by the central ECG vendor to the investigator/delegate. If specific (pre-defined in the ECG manual) ECG abnormalities are observed, the central ECG vendor will alert the sponsor and the investigator/delegate.

All ECG reports must be reviewed, signed and dated by the investigator or delegate within 10 calendar days of receipt and filed with the source documentation. The investigator/delegate must indicate on the ECG report whether abnormal values or findings are considered clinically relevant or not. Clinically relevant ECG findings that are known at the time of signing of the ICF must be recorded as medical history in the eCRF.

Details on ECG procedures (recording, transfer of data and reporting) will be provided in the ECG manual.

#### 7.2.5.4 Clinical laboratory assessments

See schedule of activities [Table 1] for the timing and frequency.

A central laboratory (see central laboratory manual for contact details) will be used for all protocol-mandated laboratory tests, including re-tests due to laboratory abnormalities and laboratory tests performed at unscheduled visits.

Exceptional circumstances that may require recording of local laboratory results (with corresponding normal ranges) include hospitalization of the study participant due to a medical emergency and missing central laboratory results from a scheduled or unscheduled visit.

If two or more consecutive central laboratory samples are lost or cannot be analyzed for whatever reason, the investigator/delegate will collect an additional sample as soon as possible for repeat analysis, unless a local laboratory sample was collected within the same time window and these test results are available.

Under specific circumstances (e.g., if the study participant lives far from the site and cannot return every month), laboratory samples may be collected at a laboratory close to where the study participant lives (satellite laboratory) and sent to the central laboratory for analysis. In such a case, the satellite laboratory must be provided with the central laboratory sampling kits. Shipment of the samples will be organized by the satellite laboratory. The supervision of the satellite laboratory remains the responsibility of the PI.

Central laboratory reports will be sent to the investigator. In the event of specific (pre-defined) laboratory abnormalities, the central laboratory will alert the sponsor personnel and the concerned site personnel. Alert flags that will trigger such notifications will be displayed in the laboratory manual.

All laboratory reports must be printed, reviewed, signed and dated by the investigator or delegate within 5 calendar days, and filed with the hospital chart. The investigator/delegate must indicate on the laboratory report whether abnormal values are considered clinically relevant or not. Clinically relevant laboratory findings that are known at the time of signing of the ICF must be recorded as medical history in the eCRF.

Blood samples will be drawn in the morning under fasted conditions (i.e., before breakfast) and when applicable before the morning administration of the study treatment at all scheduled and unscheduled visits. However, it is not permitted to request that study participants are in a fasted state (for the study) at the Screening visit unless the ICF has already been signed.

A serum pregnancy test for WOCBP will be performed at the Screening visit and EOT visit.

ACT-539313		Doc No D-21.148
Binge Eating Disorder		
Protocol ID-082A201	Confidential	
Final Version 3		
4 May 2021, page 71/140		

Urine pregnancy tests will be performed at randomization before first study treatment administration (Visit 2) and monthly thereafter (i.e., Visit 5 and Visit 7) up to EOS visit. Urine pregnancy tests will be performed with locally approved kits.

The results of the urine pregnancy tests will be collected in the eCRF. Serum pregnancy tests will be sent to the central laboratory for analysis and the result will be sent to the investigator/delegate. If pregnancy is suspected during the study, i.e., in each case of delayed menstrual period (e.g., over one month between menstruations), a serum pregnancy test must be performed as soon as possible. Reporting procedures of pregnancy are described in Section 8.3.1.

Hematology:

- Hemoglobin
- Hematocrit
- Erythrocytes
- Reticulocyte
- Leukocytes with differential counts
- Platelets.

Clinical chemistry:

- ALT
- AST
- Alkaline phosphatase
- Creatine kinase
- Total and direct bilirubin
- Gamma-glutamyl transferase
- Creatinine and estimated glomerular filtration rate
- Blood urea nitrogen
- Uric acid
- Glucose
- HbA1c
- Total cholesterol
- Triglycerides
- Sodium, potassium, chloride, calcium
- Albumin
- Thyroid hormones, i.e., triiodothyronine (total and free) and thyroxine (total and free), and TSH (Visit 1 only).

Viral serology:

• At Screening, blood sample will be collected to test for HIV, Hepatis B and C.

#### Other tests:

The urine drug screening kits (testing for presence of benzodiazepines, barbiturates, cannabinoids, opiates, amphetamines, phencyclidine or cocaine) will be provided by the central laboratory.

Details about the collection, sampling, storage, shipment procedures, and reporting of results and abnormal findings can be found in the laboratory manual.

#### 7.2.5.5 Stanford Sleepiness Scale

The SSS [Hoddes 1972, Hoddes 1973] is a self-administered questionnaire that uses a 7point Likert scale, developed to quantify the subjective sleepiness at any given time. Participants will be asked to pick the response (number) that best represents how they are feeling two times during the day: once before breakfast (i.e., before the morning dose of the study treatment) and then at midday or any time before lunch to capture daytime sleepiness temporally related to intake of study treatment. Participants will be asked to answer the paper based SSS questionnaire during the first 2 weeks after randomization. This will then be transcribed by the site into the eCRF.

#### 7.2.5.6 Benzodiazepine Withdrawal Symptom Questionnaire

The BWSQ assesses the occurrence of symptoms which might be experienced by study participants after discontinuation of treatment with ACT-539313 [Tyrer 1990]. The questionnaire consists of 20 items. The symptoms will be rated from 0 (No), 1 (Yes-moderate) to 2 (Yes-severe). The questionnaire will be self-administered using the touchscreen device at EOT visit and EOS visit.

#### 7.2.5.7 Columbia Suicide Severity Rating Scale©

The C-SSRS $^{\odot}$  is an instrument that reports the presence and severity of both suicidal ideation and behaviors.

Suicidal ideation is classified on a 5-item scale:

- 1. Wish to be dead
- 2. Non-specific active suicidal thoughts
- 3. Active suicidal ideation with any methods (no plan) without intent to act
- 4. Active suicidal ideation with some intent to act, without specific plan
- 5. Active suicidal ideation with specific plan and intent

The C-SSRS© also captures information about the intensity of ideation, specifically the frequency, duration, controllability, deterrents, and reasons for the most severe types of ideation.

In addition, the C-SSRS© captures information using yes/no questions and answers on suicidal behaviors, specifically: actual, interrupted, and aborted attempts; preparatory acts
or behaviors; and the presence of suicidal behaviors during the assessment period. More than one classification can be selected, provided they represent separate episodes. For actual attempts only, the actual or potential lethality is classified for the initial, most lethal, and most recent attempts.

At Screening the C-SSRS© will be completed for the study participant's lifetime history of suicidal ideation and behaviors and participants who answer "yes" *in the past month* to items 2, 3, 4, or 5 on the C-SSRS© assessment will be excluded from the study [see Section 5.4, criterion #26). At all other visits, the C-SSRS© will be completed for ideation and behaviors since the previous visit. All time points will be collected on a touchscreen device on site.

Participants who answer "yes" to items 2, 3, 4, or 5 on the C-SSRS© assessment at any post-randomization visit must undergo further evaluation by the investigator to assess the risk. No study treatment will be dispensed to such participants until after the investigator confirms suitability of the participant to remain in the study. This evaluation and decision should also be clearly recorded in the source documents.

As part of routine clinical care, participants will be provided with 24-hour emergency contact details in the event of an emergency should the participant feel that he/she is acutely at risk. In addition, participants who are recruited into the study will be advised of the location of their nearest hospital.

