- 20. Treatment with sensitive substrates of CYP3A4, moderate or strong inhibitors and/or inducers of CYP3A4, and sensitive substrates of CYP2C19, CYP2C8 and CYP2C9 within 2 weeks of randomization (Visit 2) or planned to be initiated during the study.

- 21. Consumption of the following fruits and their juices is not permitted within 2 weeks of randomization (Visit 2) to EOT visit: grapefruit, grapefruit hybrids, Seville orange, pomelos, pomegranates, and star fruits.
- 22. Use of medications that affect body weight or appetite, including weight loss medications, insulin, GLP-1 receptor agonists, systemic corticosteroids, over-the-counter (including herbal) medications, within 3 months prior to Screening or planned to be initiated during the study.
- 23. Known hypersensitivity to drugs of the same chemical/pharmacological class as ACT-539313, or any of its excipients.
- 24. Previous exposure to ACT-539313.

#### Criteria assessed at Visit 1 and Visit 2

- 25. HAMD-17 score  $\geq$  17 points at Visit 1 and/or Visit 2.
- 26. Any of the following conditions related to suicidality:
  - a) Participant is considered to have a suicide risk in the investigator's opinion or has a previous history of suicide attempt within the past 12 months.

b) Participant answers "yes" to "suicidal ideation" item 2 (non-specific active suicidal thoughts), item 3 (active suicidal ideation with any methods [not plan] without intent to act), item 4 (active suicidal ideation with some intent to act, without specific plan), or item 5 (active suicidal ideation with specific plan and intent) on the C-SSRS® assessment at Screening (in the past month). Participants who answer "yes" to this question must be referred to the investigator for follow-up evaluation.

- 27. Female participants: pregnant, lactating or planning to become pregnant during the projected course of the study.
- 28. Positive urine drug screen (for benzodiazepines, barbiturates, cannabinoids, opiates, amphetamines, phencyclidine, antidepressants or cocaine).

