#### 5.9.1 Study treatment premature discontinuation

The decision to prematurely discontinue study treatment may be made by the study participant, the investigator/delegate, or the sponsor personnel.

The investigator/delegate has the option of prematurely discontinuing study treatment for a given study participant in response to an AE, a diagnostic or therapeutic procedure, a laboratory abnormality, or for administrative reasons. If study treatment is interrupted by the study participant for any reason, she/he must inform the investigator/delegate as soon as possible. Study treatment dose interruptions must be recorded in the eCRF.

The investigator/delegate must permanently discontinue study treatment for a given study participant if, on balance, he/she believes that continued administration would be contrary to the best interests of the study participant.

Study-specific criteria for permanent discontinuation of study treatment are described in Sections 5.9.1.1 to 5.9.1.4.

The main reason for permanent discontinuation of study treatment (e.g., due to pre-specified study treatment discontinuation criteria, an AE, lack of efficacy, study termination) must be documented in the eCRF.

A study participant who prematurely discontinues study treatment is not considered as withdrawn from the study.

The study participant who prematurely discontinues study treatment or who is permanently discontinued from study treatment will be asked to return for an EOT visit within 1 to 5 days of last intake of study treatment and thereafter to attend follow-up visits as defined in the schedule of activities [Table 1, Section 7.2].

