# 8.2 **Reporting procedures**

# 8.2.1 Reporting and follow-up of AEs

The occurrence of an AE may come to the attention of study personnel during study visits, telephone calls, or interviews of study participants presenting for medical care.

At each study visit (scheduled or unscheduled), the investigator/delegate will inquire about the occurrence of AEs since the last visit.

All AEs with an onset date after signing of the ICF up to EOS must be recorded in the eCRF.

The AE should be reported as a final diagnosis (if possible) rather than a list of symptoms.

Information to be collected on an AE form in the eCRF includes date of onset, time of onset, action taken with the study treatment, outcome of the AE, date and time of resolution (if applicable), and PI/delegate's assessment of intensity as well as its relationship to study treatment or protocol-mandated procedures.

Information on worsening of intensity will be collected. If the AE lessens in intensity, no change in the severity is required to be reported.

AEs still ongoing after study treatment discontinuation must be followed up until resolution, until they are no longer considered clinically relevant, or until stabilization.

ACT-539313 Binge Eating Disorder Protocol ID-082A201 Final Version 3 4 May 2021, page 80/140

Confidential

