# 8.2.2 Reporting and follow-up of SAEs

All SAEs must be reported by the investigator/delegate to the sponsor's Global Drug Safety department within 24 hours of site staff's first awareness/knowledge of the event.

All SAEs occurring after signing of the ICF up to EOS must be recorded on an SAE form, regardless of the investigator/delegate-attributed causal relationship with study treatment or study-mandated procedures.

The SAE forms must be sent to the sponsor's Global Drug Safety department (see contact details on the SAE form). The investigator/delegate must complete the SAE form in English and must assess the event's causal relationship to the study treatment.

Any relevant information from source documents regarding the SAE, e.g., hospital notes or discharge summaries etc., must be summarized on the SAE form.

Follow-up information about a previously reported SAE must be promptly reported. The sponsor's Global Drug Safety personnel may contact the investigator/delegate to obtain further information.

If the study participant is hospitalized in a hospital other than that of the study site, it is the investigator/delegate's responsibility to contact this hospital to obtain all SAE-relevant information and documentation.

New SAEs occurring after EOS must be reported to the sponsor's Global Drug Safety department within 24 hours of site staff's first awareness/knowledge of the event, **only** if considered relevant and study treatment-related by the investigator/delegate.

SAEs still ongoing after EOS must be followed up until resolution, stabilization, or until the event outcome is provided.

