7.8 Columbia-Suicide Severity Rating Scale[©]

The C-SSRS[©] is an instrument that evaluates suicidal ideation and behaviors.

The C-SSRS[©] outcome categories are provided below. Each category has a binary response (yes/no).

ACT-539313		Statistical Analysis Plan
ID-082A201	Confidential	for Clinical Study Report
1 April 2022, page 37/60	Confidential	Version 3
		Doc No D-22.100

- 1 Wish to be dead
- 2 Non-specific active suicidal thoughts
- 3 Active suicidal ideation with any methods (not plan) without intent to act
- 4 Active suicidal ideation with some intent to act, without specific plan
- 5 Active suicidal ideation with specific plan and intent
- 6 Preparatory acts or behavior
- 7 Aborted attempt
- 8 Interrupted attempt
- 9 Actual attempt (non-fatal)
- 10 Completed suicide

Categories 1-5 relate to suicidal ideation and a score of 0 is assigned if no suicidal ideation is present. Categories 6-10 relate to suicidal behavior.

Self-injurious behavior without suicidal intent is also a C-SSRS[©] outcome (although not suicide-related) and has a binary response (yes/no).

Based on the C-SSRS[©], the number (%) of study participants with suicidal ideation by category, suicidal behavior by category, suicidal ideation or suicidal behavior, and/or self-injurious behavior without suicidal intent, during the treatment period and the safety follow-up period will be tabulated. Percentages will be based on the number of study participants with at least one post-baseline C-SSRS[©] assessment. The assessments done at Week 1, 2, 4, 6, 8, 10, 12 will be assigned to the treatment period while the assessment done at EOS will be assigned to the safety follow-up period.

Shift from baseline showing any change in suicidal ideation and suicidal behavior during the treatment period and the safety follow-up period will be provided. Study participants will be summarized under the worst of the following three categories, shown here in the order from best to worst: 1) No suicidal ideation or behavior, 2) Suicidal ideation, and 3) Suicidal behavior (study participants with both suicidal ideation and suicidal behavior are also included in the suicidal behavior category).

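### After randomization, the C-SSRS risk evaluation and dispensing hold are triggered only by ideation items 2 to 5, so a reported suicide attempt or preparatory act with those items negative triggers neither

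*Protocol*

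**What the plan says.** Protocol Section 7.2.5.7 describes the C-SSRS in two parts. Ideation is a numbered five-item scale, from a wish to be dead (item 1) to active ideation with a specific plan and intent (item 5). Behavior is covered by further yes/no questions on "actual, interrupted, and aborted attempts; preparatory acts" or behaviors. At every visit after Screening, both parts refer to the time since the previous visit.

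The action rule follows in the same section. Participants positive on items 2, 3, 4 or 5 on the "assessment at any post-randomization visit must undergo further evaluation by the investigator to assess the risk". The hold comes next: "No study treatment will be dispensed to such participants until after the investigator confirms suitability of the participant to remain in the study". The evaluation and decision must be recorded in the source documents. No sentence in the section attaches an action to a positive behavior answer.

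At entry the protocol looks at both parts. In Section 5.4, criterion 26a excludes a participant who "has a previous history of suicide attempt within the past 12 months", and criterion 26b excludes those positive on ideation items 2 to 5 in the past month.

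SAP Section 7.8 numbers the outcomes in the same way: 1 to 5 are ideation, and "Categories 6-10 relate to suicidal behavior". For its shift table it ranks participants from best to worst as no ideation or behavior, then ideation, then behavior.

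**The concern.** The post-randomization rule carries forward the item list from criterion 26b and leaves out the attempt history in 26a. The protocol gives no reason for the omission. The result runs against the SAP's own ranking: the middle category (ideation, apart from item 1) leads to a mandatory evaluation and a hold, and the worst category (behavior) leads to neither by itself.

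At stake is participant safety. Someone who reports an attempt or preparatory act since the last visit and answers no to items 2 to 5 can be given the next supply without a documented risk evaluation, and the protocol will have been followed exactly. Section 7.2 lets delegated physicians, specialist nurses or nurse practitioners complete the C-SSRS, so the trigger sentence is what obliges them to bring a positive result to the investigator before drug is released. For behavior answers they have no such C-SSRS instruction.

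**Working it through.** The point is mainly one of wording, so the check sets the provisions side by side. A short count then shows where the gap could act.

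**Can the item list be read to include behavior?** No. Section 7.2.5.7 numbers only the ideation items, and SAP Section 7.8 places behavior in categories 6 to 10.

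**What the rule does for each answer pattern after randomization**

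| Items 2–5 | Behavior questions | Evaluation required | Dispensing hold |
|---|---|---|---|
| Any yes | No | Yes | Yes |
| Any yes | Any yes | Yes | Yes |
| All no | Any yes | **No** | **No** |
| All no | All no | No | No |

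The hold refers back to the participants in the sentence before it, so it has the same condition as the evaluation. The third row is the gap.

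**Does another provision close it?**

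- *Treatment discontinuation, Section 5.9.1.* The investigator must stop treatment if he or she "believes that continued administration would be contrary to the best interests of the study participant". This rests on judgment and prescribes no evaluation. The study-specific criteria in 5.9.1.1 to 5.9.1.4 cover pregnancy, contraception, aminotransferases and COVID-19, not suicidality.
- *AE recording, Section 8.2.1.* The form captures "action taken with the study treatment". That documents a decision but does not require one before dispensing.
- *SAE reporting, Section 8.2.2.* "All SAEs must be reported by the investigator/delegate to the sponsor's Global Drug Safety department within 24 hours" of first awareness. This informs the sponsor and does not hold supply.
- *Remote visits, Section 7.2.5.8.* The investigator may consider discontinuation if closer monitoring is needed but not possible. This is optional.
- *Benefit/risk monitoring (Section 2.4), sponsor safety review (Section 10.9) and emergency contacts (Section 7.2.5.7).* None is tied to a behavior answer.

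None of these requires a suicide-risk evaluation or a hold.

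**Where the gap could act** (schedule of activities, Table 1; two capsules a day)

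- C-SSRS visits after randomization: Weeks 1, 2, 4, 6, 8, 10, 12/EOT and EOS = **8** (evaluation).
- Of these, visits that dispense further treatment: Weeks 1, 2, 4, 6, 8 and 10 = **6** (hold).
- Supply to the next planned visit: Week 1 (Day 8 to Day 15) = 7 × 2 = 14 capsules. Weeks 2, 4, 6, 8 and 10 (Days 15, 29, 43, 57 and 71, each 14 days to the next visit) = 14 × 2 = 28 capsules each.
- Planned total: 84 × 2 = 168 capsules.
- One missed hold: 14/168 = 8.3% or 28/168 = 16.7% of planned supply.
- All supply dispensed at the six visits: 14 + 5 × 28 = 154; 154/168 = 91.7%. The other 14 capsules are dispensed on Day 1, before any post-randomization C-SSRS.

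The 91.7% is the share of supply that the hold could in principle govern, not an expected exposure. The count assumes that supply exactly covers the planned interval, because bottle size is not given.

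**The case against.** The best argument against is that the pattern should be unusual. Ideation and behavior refer to the same interval, and SAP Section 7.8 lists self-injury without suicidal intent separately, so the behavior categories are the suicide-related ones. Most people who report such behavior would be expected to answer yes at least to item 2, which meets both triggers. This stands as a reason to expect few cases. It does not justify leaving the pattern out, since the questions are asked separately and can be answered discordantly.

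Second, trained staff record the answers, classify lethality for actual attempts, and work under the general duties listed above. Many investigators would act anyway. That is fair, but the same duties apply to item 2 thoughts, and there the protocol still added a specific evaluation and hold. Section 8.1.1 defines adverse events broadly, so an attempt would very likely be recorded and, if serious, reported within 24 hours. Recording and reporting still hold no supply.

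Third, the 91.7% could be misread as exposure caused by the gap. For one participant on one occasion the relevant figure is 14 or 28 capsules.

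Fourth, Appendix 12 (the instrument) is not shown in the public copy, and the touchscreen manual is not among the documents. Escalation instructions there could not be checked.

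**Conclusion.** The concern holds. As written, Section 7.2.5.7 requires neither a risk evaluation nor a dispensing hold when suicidal behavior is reported with items 2 to 5 answered no, and no other visible provision requires either. The claim is limited to the C-SSRS-specific triggers and does not say that participants are without safeguards.

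The gap covers eight visits for the evaluation and six for the hold. Its frequency cannot be estimated from the documents. Criterion 26 and the overlap between ideation and behavior should make cases few among about 120 participants. The primary endpoint, power and planned analyses are not affected. The point should be fixed because the outcome, though rare, can be grave and the correction is small. Confidence is high for the wording of Section 7.2.5.7. Whether site materials fill the gap is unknown.

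**What to change.** In the trigger sentence of Protocol Section 7.2.5.7, add after the list of items: *or to any suicidal behavior question (actual, interrupted or aborted attempt, or preparatory acts or behavior)*. The hold and source-documentation sentences refer back to the same participants and then apply unchanged. Site training and any escalation text in the touchscreen materials should be aligned with it.

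No new assessment, data field or analysis is needed, because the behavior answers are already collected at each visit. The cost is a short protocol amendment, which Section 10.1 requires to be submitted to the IEC/IRB and the health authority under local procedures. The SAP is dated 1 April 2022 and the documents do not show whether participants are still on treatment. If dosing has ended, the clause belongs in the protocols of the later studies that Section 4.3 foresees.
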